• Pharmacokinetic (PK) profiles of SJP-0132	• Part A: C_{max} , t_{max} , t_{last} , AUC_{0-last} , $AUC_{0-\infty}$, $t_{1/2}$, $AUC_{\%extrap}$, $AUMC_{0-last}$, $AUMC_{0-\infty}$, MRT_{0-last} , $MRT_{0-\infty}$, Vd/F , CL/F , $C_{max,norm}$, $AUC_{0-last,norm}$, and $AUC_{0-\infty,norm}$ • Part B: C_{max} , t_{max} , t_{last} , AUC_{0-last} , $C_{max,norm}$, and $AUC_{0-last,norm}$ on Day 1, C_{trough} on Days 2, 4 and 8, and Rac
• Efficacy of SJP-0132	• Change from baseline (predose on Day 1) in eye dryness symptom (visual analog scale [VAS]) at 4 hours on Day 29 • Change from baseline (predose on Day 1) in corneal fluorescein staining (CFS) score at the central zone on Day 29
Secondary	
• Efficacy of SJP-0132	• Changes from baseline in dry eye signs: CFS scores at the central, superior, inferior, nasal, temporal and total zones,

[figure not shown]
	
conjunctival lissamine green staining (CLGS) scores at each of 3 nasal and 3 temporal zone and total zone of bulbar conjunctiva, lid wiper epitheliopathy score, and tear film break-up time (TFBUT) at each time point tested
 
 Changes from baseline in dry eye symptoms (VAS [ie, severity of eye dryness, discomfort, burning/stinging, sticky feeling, foreign body sensation, itching, pain, blurred vision, and sensitivity to light], ocular surface disease index [OSDI[®]], Dry eye Questionnaire 5 [DEQ-5] scores) at each time point tested Biomarker (Matrix Metalloproteinase-9 (MMP-9), InflammaDry[®])
--	--

Overall Design:

[figure not shown]
This is a randomized, double-masked, placebo-controlled single and multiple ascending dose study of SJP-0132 in subjects with dry eye disease who have frequent ocular discomfort or dryness. Non-Japanese subjects will be enrolled in Part A and both Japanese and non-Japanese subjects will be enrolled in Part B.

After Screening (including review of laboratory results), placebo medication will be dispensed to all eligible subjects to be instilled as one drop in each eye [REDACTED] (Placebo Run-In Phase). Subjects will be admitted to the study center on Day -1 and undergo physical and ophthalmic examinations as shown in [Section 2, Schedule of Activities](#).

Part A

Part B

Part A

In Part A, 32 non-Japanese subjects will be admitted to the study center on Day -1 and discharged on Day 2 after completion of assessments and blood collections. Subjects will be randomized to receive a single dose of placebo or SJP-0132 ophthalmic [REDACTED] concentrations of 0.03%, 0.1%, 0.3%, or 1% on Day 1 after confirmation of continued eligibility. All treatments will be administered in both eyes.

Blood for PK measurements will be collected before dosing and at the timepoints specified in the Schedule of Activities (SoA). Eye and safety assessments will be done as indicated below.

After each cohort completes the single dose of SJP-0132 ophthalmic [REDACTED] or placebo, the Investigator and the Sponsor will assess the data to confirm adequate safety and tolerability while the next cohort begins the Run-in Phase. A written report will be provided.

After completion of the single dose cohorts, a safety review will be conducted to identify the maximum acceptable dose and the second maximum acceptable dose of study drug. The maximum and second maximum acceptable doses of study drug will be selected for the multiple dose study (Part B) in subjects with dry eye disease. Maximum acceptable dose is the highest dose at which no more than 1 subject experiences a severe drug-related AE.

Part B

In Part B, 60 Japanese and non-Japanese subjects will be admitted to the study center on Day -1 and discharged on Day 8 after completion of assessments and blood collections. Subjects will be randomized to receive placebo or SJP-0132 ophthalmic [REDACTED] on Day 1 after confirmation of continued eligibility.

The first cohort randomized in Part B (Cohort 5) will receive the second maximum acceptable concentration of SJP-0132 ophthalmic [REDACTED] or placebo [REDACTED] [REDACTED] for 4 weeks. The second cohort randomized in Part B (Cohort 6) will receive the maximum acceptable dose of SJP-0132 ophthalmic [REDACTED] or placebo [REDACTED] for 4 weeks. All treatments will be administered in both eyes.

After Cohort 5 completes the 7-day inpatient assessment of SJP-0132 ophthalmic [REDACTED] or placebo, the Investigator and the Sponsor will assess the data (AEs, clinical laboratory results, vital signs, ophthalmic examinations) to confirm adequate safety and tolerability before allowing a cohort of the next dose level (Cohort 6) to begin. A written report will be provided.

All subjects who complete the Day 29 ± 2 EOS visit, will receive a follow-up telephone call on Day 36 ± 2 to review AEs and medication use.

For any subjects who receive at least one dose of study drug and discontinue or withdraw from study participation prior to the Day 29 ± 2 EOS visit, subjects should complete the EOS visit at the time of discontinuation/withdrawal. Discontinued/withdrawn subjects will also be contacted by telephone 7 days later for follow-up.

Pharmacokinetic (PK) blood draws will be collected prior to dosing on Days 1, 2, 4, and 8, and after dosing on Day 1 at timepoints specified in SoA.

For all subjects in Part A and Part B, the following eye assessments will be done according to the SoA: VAS, visual acuity (by Snellen), corneal aesthesiometry (Cochet-Bonnet),DEQ-5, OSDI®,

slit-lamp biomicroscopy, VAS with anesthesia, intraocular pressure (iCare), fluorescein staining (Baylor Scales), lissamine green staining (Baylor Scales +lid margins [lid wiper epitheliopathy]), Schirmer I test (without anesthesia), tear film break up time (TFBUT), ophthalmoscopy, and matrix metalloproteinase-9 (MMP-9). All ocular exams will be completed for both eyes (study eye and non-study eye) at all timepoints.

For all subjects in Part A and Part B, the following safety assessments will include changes in vital signs (blood pressure, heart rate, oral body temperature (°C), respiratory rate), clinical laboratory results (hematology, clinical chemistry, and urinalysis), adverse events (AEs), concomitant medication use, physical examinations. Additionally, the subjects' overall ocular irritation will be assessed.

In case any medically significant suspected adverse reactions or findings are observed, the Data and Safety Monitoring Board (i.e., consisting of the Investigator, Sponsor, and pharmacovigilance physician) will make a decision for future course of action.

Number of Subjects:

Approximately 226 subjects will be screened to achieve 32 completers in treatment in Part A and 60 completers in Part B.

Treatment Groups and Duration:

Part A: 4 cohorts consisting of 8 subjects each (non-Japanese), with 6 subjects randomized to SJP-0132 ophthalmic [REDACTED] and 2 randomized to placebo.

- Cohort 1: 0.03% SJP-0132 / Placebo
- Cohort 2: 0.1% SJP-0132 / Placebo
- Cohort 3: 0.3% SJP-0132 / Placebo
- Cohort 4: 1% SJP-0132 / Placebo

Part B: 2 cohorts consisting of 30 subjects each (9 Japanese and 21 non-Japanese) 20 randomized to SJP-0132 ophthalmic [REDACTED] and 10 randomized to placebo

Cohort#	Active		Placebo		Total
	JP	Non-JP	JP	Non-JP	
5	6	14	3	7	30
6	6	14	3	7	30
Total	12	28	6	14	60

JP = Japanese

For Part A, subject participation will be approximately 32 days, including Screening. For Part B, subject participation will be approximately 9 weeks, including Screening. Total study duration is anticipated to be 3 months.

Investigational Product, Dose, and Mode of Administration

One drop of SJP-0132 ophthalmic [REDACTED] instilled in both eyes [REDACTED]

Statistical Methods

The primary statistical analysis of the data will be descriptive in nature. For continuous variables this means calculation of the number of observations, mean, standard deviation, median, minimum, and maximum. Categorical variables will be summarized by subject counts and related percentages. For ordinal-scaled variables, a combination of the above may be employed as appropriate: frequency and percentage of observations within a category and means and standard deviations of the scores of the categories. For categorical and ordinal variables, percentages will be calculated based on non-missing data.

Sample Size Determination:

No formal sample size and/or power calculations were performed for the study, however a sample size was chosen based on feasibility to allow total of 92 randomized subjects for Part A (n=32) and Part B (n=60). Approximately 32 subjects are expected to complete Part A and 60 subjects are expected to complete Part B.

Safety Analysis:

Safety assessments and changes from baseline in vital signs, clinical laboratory results, adverse events (AEs), will be summarized using descriptive statistics (mean, standard deviation, coefficient of variation (%CV), median, minimum, and maximum). Concomitant medications and physical examination findings will be listed.

Efficacy Analysis:

The study eye will be the eye with the greater central zone corneal fluorescein staining. If both eyes meet all of the inclusion and none of the exclusion criteria and the central zone corneal fluorescein staining scores are equal, the right eye (OD) will be designated as the study eye for the duration of this study.

The fellow eye (non-study eye) will be treated with the product as per the assigned dosing schedule.

Change in eye assessments will be summarized using descriptive statistics (mean, standard deviation, coefficient of variation (%CV), median, minimum, and maximum). The primary endpoint is the difference between SJP-0132 and placebo in changes in eye dryness symptom (visual analog scale [VAS]). Secondary endpoints are changes in dry eye signs (vital staining of cornea, conjunctiva and lid margin, tear film break-up time (TFBUT), and changes in dry eye symptoms (VAS [ie, severity of eye dryness, discomfort, burning/stinging, sticky feeling, foreign body sensation, itching, pain, blurred vision, and sensitivity to light], ocular surface disease index [OSDI[®]], Dry eye Questionnaire 5 [DEQ-5] scores).

Pharmacokinetic Analysis:

Plasma samples will be analyzed to determine the concentration of SJP-0132. Pharmacokinetic variables will be calculated using non-compartmental analysis. Part A: C_{max} , t_{max} , t_{last} , AUC_{0-last} , $AUC_{0-\infty}$, $AUC_{\%extrap}$, $t_{1/2}$, $AUMC_{0-last}$, $AUMC_{0-\infty}$, MRT_{0-last} , $MRT_{0-\infty}$, Vd/F , CL/F , $C_{max,norm}$, $AUC_{0-last,norm}$, $AUC_{0-\infty,norm}$. Part B: C_{max} , t_{max} , t_{last} , AUC_{0-last} , $C_{max,norm}$, and $AUC_{0-last,norm}$ on Day 1, C_{trough} on Days 2, 4 and 8, and Rac . The PK data will be summarized using descriptive statistics and will also be displayed graphically as appropriate.

2. Schedule of Activities (SoA)

Part A (SAD)	Screen	Run-in	Check In	Treatment Phase						Check Out
				Day 1						
Procedure	Day -30 to Day -15	Day -14 (+2) ⁵ to Day -2	Day -1	0 h	0.25 h	1 h	2 h	4 h	8 h	12 h
Informed Consent / HIPAA	X									
Demography	X									
Medical / Surgical History	X		X							
Inclusion/Exclusion Criteria	X		X							
Physical Examination ¹	X			X		X				X
Height	X									
Weight	X		X							
Vital signs ²	X		X	X	X	X	X	X	X	X
DEQ-5 ³	X		X							
VAS ³	X		X	X	X	X	X	X	X	X
OSDI ^{®3}	X		X							
Hematology, Serum Chemistry, Urinalysis	X		X							X
Serology (HIV, HBsAg, HCV)	X									
Serum pregnancy test and FSH (WOCBP only)	X									
Pharmacokinetic Sampling				X	X	X	X	X	X	X
Urine drug and alcohol screen	X		X							
Urine Pregnancy Test			X							
Visual Acuity (Snellen)	X		X							X X
Slit lamp biomicroscopy (w/out mydriatics)	X			X		X	X			X X
Matrix Metalloproteinase-9 (MMP-9) ⁴	X		X							
TFBUT	X			X			X			X X
Corneal fluorescein staining (Baylor)	X		X	X			X			X X
Lissamine green staining (Baylor + Lid Margin)	X			X						
Aesthesiometer	X									
Schirmer I w/o anesthesia	X		X							X X
VAS w/ anesthesia	X									
Intraocular Pressure (iCare tonometer)	X			X			X			X X
Slit lamp biomicroscopy (w/ mydriatics; lens observation)	X		X							X X
Ophthalmoscopy	X		X							X X
Record and assess adverse events										Continuous
Concomitant Medications										Continuous
Confinement Period										X
Randomization					X					
Drug Administration		Placebo ⁶	Placebo ⁶	X						

HIPAA = Health Information Portability and Accountability Act; VAS = Visual Analog Scale; TFBUT = Tear film break-up time; OSDI = Ocular Surface Disease Index; WOCBP = women of child-bearing potential

¹ Physical Examination includes head-eye-ears-nose-throat, cardiovascular, respiratory, gastrointestinal, dermatologic, and neurologic examinations.

² Blood pressure, heart rate, respiratory rate, oral temperature.

³ Questionnaires will be completed prior to lab or PK timepoints. Ophthalmic assessments will follow lab or PK timepoints.

⁴ 30 minutes before staining tests

⁵ Day -14 can be completed within +2 days (Day -14 to Day -16), however Placebo Run-In dosing will begin on Day -14 per protocol

⁶ For Placebo Run-In (Day -14 visit) subjects will be dispensed placebo and educated in administration and dosing diary completion.

Part B (MAD) (3 pages)	Screen	Run-In	Check In	Treatment Period												
				Day 1						Day 2				Day 3		
				0 h	0.25 h	0.5 h	1 h	2 h	4 h	8 h	12 h	0 h	4 h	8 h	12 h	
Informed Consent/HIPAA	X															
Demography	X															
Medical/Surgical history	X		X													
Inclusion/Exclusion Criteria	X		X													
Physical examinations ¹	X			X			X					X		X		
Height	X															
Weight	X		X													
Vital signs ²	X		X	X		X	X	X	X	X	X	X	X	X	X	X
DEQ-5 ³	X		X													
VAS ³	X		X	X		X	X	X	X	X	X	X	X	X	X	X
OSDI ^{© 3}	X		X													
Hematology, Serum Chemistry, Urinalysis	X		X													
Serology (HIV, HBsAg, HCV)	X															
Serum pregnancy test and FSH (WOCBP only)	X															
Pharmacokinetic Sampling					X	X	X	X	X	X		X				
Urine drug and alcohol screen	X		X													
Urine pregnancy test			X													
Visual acuity (Snellen)	X		X									X	X		X	
Slit lamp biomicroscopy (w/out mydriatics)	X			X			X	X				X	X		X	X
Matrix Metalloproteinase-9 (MMP-9) ⁴	X		X													
TFBUT	X			X				X				X	X		X	X
Corneal fluorescein staining (Baylor)	X		X	X				X				X	X		X	X
Lissamine green staining (Baylor +Lid Margin)	X			X								X	X		X	X
Aesthesiometer	X															
Schirmer I w/o anesthesia	X		X									X	X			
VAS w/ anesthesia	X															
Intraocular pressure (iCare tonometer)	X			X								X	X		X	
Slit lamp biomicroscopy (w/ mydriatics; lens observation)	X		X									X				
Ophthalmoscopy	X		X									X				
Record and assess adverse events												Continuous				

Part B (MAD) (3 pages)	Screen	Run-In	Check In	Treatment Period															
				Day 1						Day 2				Day 3					
				0 h	0.25 h	0.5 h	1 h	2 h	4 h	8 h	12 h	0 h	4 h	8 h	12 h				
Concomitant medications				Continuous															
Confinement Period				Day -1 until Day 8															
Randomization				X															
Drug administration		Placebo ⁶	Placebo ⁶	X						X	X	X	X	X	X	X	X	X	X

HIPAA = Health Information Portability and Accountability Act; VAS = Visual Analog Scale; TFBUT = Tear film break-up time; OSDI = Ocular Surface Disease Index; WOCBP = women of childbearing potential; FSH = follicle stimulating hormone

¹ Physical Examination includes head-eye-ears-nose-throat, cardiovascular, respiratory, gastrointestinal, dermatologic, and neurologic examinations.

² Blood pressure, heart rate, respiratory rate, oral temperature.

³ Questionnaires will be completed prior to lab or PK timepoints. Ophthalmic assessments will follow lab or PK timepoints.

⁴ 30 minutes before staining tests

⁵ Day -14 can be completed within +2 days (Day -14 to Day -16), however Placebo Run-In will begin on Day -14, per protocol

⁶ For Placebo Run-In (Day -14 visit) subjects will be dispensed placebo and will be educated in self -administration and dosing diary completion.

Part B (MAD) (3 Pages)	Treatment Period (continued)												EOS		Follow Up	
	Day 4 to Day 7			Day 8 (Check Out)			Day 9 to Day 28 dosing			Outpatient Visit Days 15±2, 22±2			Day 29±2	Day 36±2		
Procedure All 0h assessments will be performed prior to Drug administration.	0 h	4 h	8 h	12 h	0 h	4 h	8 h	12 h	0 h	4 h	8 h	12 h	0 h	2 h	4 h	8 h
Physical examinations ¹	X				X								X			
Weight																X
Vital signs ²	X				X								X			X
DEQ-5 ³																X
VAS ^{3,4}	X	X	X	X	X	X	X						X	X	X	X
OSDI ^{© 3}						X							X			X
Hematology, Serum Chemistry, Urinalysis						X										X
Serum pregnancy test (for WOCBP only)																X
Pharmacokinetic Sampling	X ⁵					X										
Visual Acuity (Snellen)	X					X							X			X
Slit lamp biomicroscopy w/out mydriatics	X				X	X							X			X
Matrix Metalloproteinase-9 (MMP-9) ⁶																X
TFBUT	X				X	X							X			X
Corneal fluorescein staining (Baylor)	X				X	X							X			X
Lissamine green staining (Baylor +Lid Margin)	X				X	X							X			X
Schirmer I w/o anesthesia						X										X
Intraocular pressure (iCare tonometer)						X							X			X
Slit lamp biomicroscopy w/ mydriatics (lens observation)						X										X
Ophthalmoscopy						X										X
Record and assess adverse events													Continuous			
Concomitant medications													Continuous			
Confinement Period		X														
Drug administration	X		X	X	X	X	X	X	X	X	X	X	X	X	X	
Telephone call																X

EOS = End of Study Assessments; VAS = Visual Analog Scale; TFBUT = Tear film break-up time; OSDI = Ocular Surface Disease Index; WOCBP = women of childbearing potential

¹ Physical Examination includes head-eye-ears-nose-throat, cardiovascular, respiratory, gastrointestinal, dermatologic, and neurologic examinations.

² Blood pressure, heart rate, respiratory rate, oral temperature.

³ Questionnaires will be completed prior to lab or PK timepoints. Ophthalmic assessments will follow lab or PK timepoints.

⁴ VAS assessment completed on Day 4 & 7 at 0h, 0.5h, 1h, 2h, 4h, 8h, 12h timepoints. VAS on Days 5 & 6 at 0, 4, 8, and 12 h

⁵ Day 4 only

[figure not shown]
⁶ 30 minutes before staining tests

[figure not shown]
⁷ Check-out after completion of all Day 8 assessments and 0 h dosing

3. Introduction

Dry Eye Disease (DED) is defined by the International Dry Eye Workshop (DEWS) as a multifactorial disease of the ocular surface characterized by a loss of homeostasis of the tear film, and accompanied by ocular symptoms, in which tear film instability and hyperosmolarity, ocular surface inflammation and damage, and neurosensory abnormalities play etiological roles. It is one of the most frequently encountered ocular morbidities. Twenty-five percent of patients who visit ophthalmic clinics report symptoms of dry eye, making it a growing public health problem and one of the most common conditions seen by eye care practitioners ([Gayton 2009](#)). DED is seen with increased prevalence in patients with autoimmune diseases ([Fox 1984](#)), which affect approximately 8% of the population, of whom 78% are women ([Fairweather 2008](#)). DED also affects postmenopausal women ([Schaumberg 2003](#)) and the elderly ([Moss 2000](#), [Lin 2003](#)). The prevalence of symptomatic dry eye in the United States is about 7% in women and 4% in men over the age of 50 years ([Schaumberg 2003](#)). These numbers translate into approximately 3.2 million women and 1.05 million men with DED in the United States ([Schaumberg 2002](#)). The prevalence of DED in Japan is estimated to be 33% ([Shimmura 1999](#)).

Initial treatments for DED are recommended environmental and lifestyle changes, and the use of artificial tears, Restasis®, or topical steroids. Steroids help control DED-associated inflammation, but they should not be used long term because of their possible role in elevating intraocular pressure (IOP) and causing cataracts. The two main issues associated with the use of Restasis are burning, which is very significant in some patients, and the relatively long onset of action that does not provide immediate relief.

[figure not shown]

[figure not shown]

[figure not shown]
3.1. Study Rationale

This is the first study in humans to evaluate the efficacy of SJP-0132 in the treatment of dry eye disease. This study will evaluate the safety, tolerability, efficacy, and pharmacokinetics (PK) of single- and multiple-dose regimens of SJP-0132

3.2. Background

4. Objectives and Endpoints

Objectives	Endpoints
Primary	
• Safety and tolerability of SJP-0132	
 The number and severity of AEs including abnormal changes in clinical laboratory results, vital signs, and physical and ophthalmologic examinations
• Pharmacokinetic (PK) profiles of SJP-0132	
 Part A: C_{max}, t_{max}, t_{last}, AUC_{0-last}, $AUC_{0-\infty}$, $t_{1/2}$, $AUC_{\%extrap}$, $AUMC_{0-last}$, $AUMC_{0-\infty}$, MRT_{0-last}, $MRT_{0-\infty}$, Vd/F, CL/F, $C_{max,norm}$, $AUC_{0-last,norm}$, and $AUC_{0-\infty,norm}$ Part B: C_{max}, t_{max}, t_{last}, AUC_{0-last}, $C_{max,norm}$, and $AUC_{0-last,norm}$ on Day 1, C_{trough} on Days 2, 4 and 8, and Rac
• Efficacy of SJP-0132	
 Change from baseline (predose on Day 1) in eye dryness symptom (visual analog scale [VAS]) at 4 hours on Day 29 Change from baseline (predose on Day 1) in corneal fluorescein staining (CFS) score at the central zone on Day 29
Secondary	
• Efficacy of SJP-0132	
 Changes from baseline in dry eye signs: CFS scores at the central, superior, inferior, nasal, temporal and total zones, conjunctival lissamine green staining (CLGS) scores at each of 3 nasal and 3 temporal zone and total zone of bulbar conjunctiva, lid wiper epitheliopathy score, and tear film break-up time (TFBUT) at each time point tested Changes from baseline in dry eye symptoms (VAS [ie, severity of eye dryness, discomfort, burning/stinging, sticky feeling, foreign body sensation, itching, pain, blurred vision, and sensitivity to light], ocular surface disease index [OSDI[®]], Dry eye Questionnaire 5 [DEQ-5] scores) at each time point tested Biomarker (Matrix Metalloproteinase-9 (MMP-9), InflammaDry[®])

5. Study Design

5.1. Overall Design

This is a randomized, double-masked, placebo-controlled single and multiple ascending dose study of SJP-0132 in subjects with dry eye disease who have frequent ocular discomfort or dryness. Non-Japanese subjects will be enrolled in Part A and both Japanese and non-Japanese subjects will be enrolled in Part B.

After Screening (including review of laboratory results), placebo medication will be dispensed to all eligible subjects to be instilled [REDACTED] (Placebo Run-In) Subjects will be admitted to the study center on Day -1 and undergo physical and ophthalmic examinations as shown in [Section 2, Schedule of Activities](#).

Part A

In Part A, 32 non-Japanese subjects will be admitted to the study center on Day -1 and discharged on Day 2 after completion of assessments and blood collections. Subjects will be randomized to receive a single dose of placebo or SJP-0132 ophthalmic [REDACTED] concentrations of 0.03%, 0.1%, 0.3%, or 1% on Day 1 after confirmation of continued eligibility. All treatments will be administered in both eyes.

Blood for PK measurements will be collected before dosing and at the timepoints specified in the [Schedule of Activities \(SoA\)](#). Eye and safety assessments will be done as indicated below.

After each cohort completes the single dose of SJP-0132 ophthalmic [REDACTED] or placebo, the Investigator and the Sponsor will assess the data to confirm adequate safety and tolerability while the next cohort begins the Run-in Phase. A written report will be provided.

After completion of the single dose cohorts, a safety review will be conducted to identify the maximum acceptable dose and the second maximum acceptable dose of study drug. The maximum and second maximum acceptable doses of study drug will be selected for the multiple dose study (Part B) in subjects with dry eye disease. Maximum acceptable dose is the highest dose at which no more than 1 subject experiences a severe drug-related AE.

Part B

In Part B, 60 Japanese and non-Japanese subjects will be admitted to the study center on Day -1 and discharged on Day 8 after completion of assessments and blood collections. Subjects will be randomized to receive placebo or SJP-0132 ophthalmic [REDACTED] on Day 1 after confirmation of continued eligibility.

The first cohort randomized in Part B (Cohort 5) will receive the second maximum acceptable concentration of SJP-0132 ophthalmic [REDACTED] or placebo [REDACTED] [REDACTED] for 4 weeks. The second cohort randomized in Part B (Cohort 6) will receive the maximum acceptable dose of SJP-0132 ophthalmic [REDACTED] or placebo [REDACTED] for 4 weeks. All treatments will be administered in both eyes.

After Cohort 5 completes the 7-day inpatient assessment of SJP-0132 ophthalmic [REDACTED] or placebo, the Investigator and the Sponsor will assess the data (AEs, clinical laboratory results, vital signs, ophthalmic examinations) to confirm adequate safety and tolerability before allowing a cohort of the next dose level (Cohort 6) to begin. A written report will be provided.

All subjects who complete the Day 29 ± 2 EOS visit, will receive a follow-up telephone call on Day 36 ± 2 to review AEs and medication use.

For any subjects who receive at least one dose of study drug and discontinue or withdraw from study participation prior to the Day 29 ± 2 EOS visit, subjects should complete the EOS visit at the time of discontinuation/withdrawal. Discontinued/withdrawn subjects will also be contacted by telephone 7 days later for follow-up.

Pharmacokinetic (PK) blood draws will be collected prior to dosing on Days 1, 2, 4, and 8, and after dosing on Day 1 at timepoints specified in SoA.

For all subjects in Part A and Part B, the following eye assessments will be done according to the SoA: VAS, visual acuity (by Snellen), corneal aesthesiometry (Cochet-Bonnet), DEQ-5, OSDI[®], slit-lamp biomicroscopy, VAS with anesthesia, intraocular pressure (iCare), fluorescein staining (Baylor Scales), lissamine green staining (Baylor Scales +lid margins [lid wiper epitheliopathy]), Schirmer I test (without anesthesia), and tear film break up time (TFBUT), ophthalmoscopy, and matrix metalloproteinase-9 (MMP-9). All ocular exams will be completed for both eyes (study eye and non-study eye) at all timepoints.

For all subjects in Part A and Part B, the following safety assessments will include changes in vital signs (blood pressure, heart rate, oral body temperature (°C), respiratory rate), clinical laboratory results (hematology, clinical chemistry, and urinalysis), adverse events (AEs), concomitant medication use, physical examinations. Additionally, the subjects' overall ocular irritation will be assessed.

In case any medically significant suspected adverse reactions or findings are observed, the Data and Safety Monitoring Board (i.e., consisting of the Investigator, Sponsor, and pharmacovigilance physician) will make a decision for future course of action.

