5.4. Scientific Rationale for Study Design

Studies comparing the pharmacokinetics and safety of a drug product in Japanese and non-Japanese (eg, Caucasian) subjects allow for extrapolation of clinical data across regions. Randomization and masking minimizes bias in the assessment of safety and interpretation of results. Safety and tolerability can be clearly assessed as each subject in Part A will receive only a single dose of SJP-0132 in an ascending fashion.

6. Study Population

A sufficient number of subjects will be screened and will participate in the study. Prospective approval of protocol deviations to recruitment and enrollment criteria, also known as protocol waivers or exemptions, is not permitted.

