7.1. Treatments Administered

For both Part A and Part B, starting at Day -14 (Placebo Run-In), subjects will instill 1 drop of Placebo into each eye [REDACTED]

In Part A, subjects will instill 1 drop of SJP-0132 or placebo into each eye (one time only).

In Part B, subjects will instill 1 drop of SJP-0132 or placebo into each eye [REDACTED]

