7.5. Method of Treatment Assignment

Subjects will be randomly assigned to SJP-0132 or placebo using a computer-generated randomization scheme.

Part A: 4 cohorts consisting of 8 subjects each (non-Japanese), with 6 subjects randomized to SJP-0132 ophthalmic [REDACTED] and 2 randomized to placebo.

- Cohort 1: 0.03% SJP-0132 / Placebo
- Cohort 2: 0.1% SJP-0132 / Placebo
- Cohort 3: 0.3% SJP-0132 / Placebo
- Cohort 4: 1% SJP-0132 / Placebo

Part B: 2 cohorts consisting of 30 subjects each (9 Japanese and 21 non-Japanese) 20 randomized to SJP-0132 ophthalmic [REDACTED] and 10 randomized to placebo:

Cohort#	Active		Placebo		Total
	JP	Non-JP	JP	Non-JP	
5	6	14	3	7	30
6	6	14	3	7	30
Total	12	28	6	14	60

JP = Japanese

Doses selected for Part B will be determined after evaluation of safety and tolerability in Part A. The first cohort randomized in Part B (Cohort 5) will receive the second maximum acceptable concentration of SJP-0132 ophthalmic [REDACTED] or placebo [REDACTED]

[REDACTED] 4 weeks. The second cohort randomized in Part B (Cohort 6) will receive the maximum acceptable dose of SJP-0132 ophthalmic [REDACTED] or placebo [REDACTED] for 4 weeks.

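### The maximum acceptable dose is defined without requiring lower doses to be acceptable, so if the reviews let escalation pass a failed dose, the written rule can send a higher dose into Part B

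*Combined protocol and SAP*

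**What the plan says.** Part A gives single doses of 0.03%, 0.1%, 0.3% and 1% in successive cohorts. Section 7.5 sets out "4 cohorts consisting of 8 subjects each (non-Japanese), with 6 subjects randomized to SJP-0132" in each cohort, with the other 2 on placebo.

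Section 5.1 places dose selection at the end of Part A: "After completion of the single dose cohorts, a safety review will be conducted to identify the maximum acceptable dose" and the second maximum acceptable dose. It gives one criterion, repeated in the synopsis: "Maximum acceptable dose is the highest dose at which no more than 1 subject experiences a severe drug-related AE". The second maximum acceptable dose has no definition of its own. The maximum dose goes to Cohort 6 and the second maximum to Cohort 5, each for 4 weeks in both eyes.

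Several reviews surround this rule:
- After each Part A cohort, the investigator and the sponsor "will assess the data to confirm adequate safety and tolerability while the next cohort begins the Run-in Phase", and a written report follows. Section 7.1 makes clear that the waiting cohort receives only placebo in that period: "starting at Day -14 (Placebo Run-In), subjects will instill 1 drop of Placebo into each eye".
- If a medically significant suspected reaction is seen, a safety board "will make a decision for future course of action".
- Section 7.5 says that Part B doses are settled once Part A safety and tolerability have been evaluated.
- Cohort 5 is reviewed after its inpatient week "to confirm adequate safety and tolerability before allowing a cohort of the next dose level (Cohort 6) to begin".

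**The concern.** In a dose-escalation study, the maximum acceptable dose is normally the top of an unbroken run of acceptable doses. The written definition does not say so. It asks only for the highest dose that meets the limit, so a dose above a failed one can qualify. With 6 active subjects per dose, a failed dose can be followed by a passing one by chance, even when the true risk rises with dose.

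The definition fixes the repeated-dose exposure of 40 active subjects (20 in each of Cohorts 5 and 6). If escalation had continued past a failed dose, the wording would support choosing a higher concentration for four weeks when the usual cautious choice is a lower one.

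**Working it through.** The plan gives no operating characteristic for this rule and no severe-event risk, so there is no figure to reproduce. All risks below are assumptions.

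**Inputs.** 6 active subjects per dose (section 7.5); four doses; a dose fails when 2 or more subjects have a severe drug-related AE (section 5.1). Events are taken as independent and only active subjects are counted.

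**Step 1: literal reading.** With counts 0, 0, 2, 1, the doses 0.03%, 0.1% and 1% meet the limit and 0.3% does not. The highest that meets it is 1%. The next is 0.1%. With a lower-dose condition, the maximum would be 0.1% and the second maximum 0.03%.

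**Step 2: chance that one dose fails.** P(fail) = 1 − (1 − p)^6 − 6p(1 − p)^5. At p = 0.05 this is 1 − 0.7351 − 0.2321 = 0.0328.

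| True risk p | 1% | 2% | 5% | 10% | 15% | 20% |
|---|---|---|---|---|---|---|
| P(fail) | 0.0015 | 0.0057 | 0.0328 | 0.1143 | 0.2235 | 0.3446 |

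**Step 3: selection above any failed dose.** Four doses give 16 pass/fail patterns. In 5 of them every pass lies below every fail; in the other 11 a passing dose lies above a failed one. Writing s for pass and f for fail at doses 1 to 4:

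P(selection above a failed dose) = 1 − [s1s2s3s4 + s1s2s3f4 + s1s2f3f4 + s1f2f3f4 + f1f2f3f4]

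At 2/5/10/15%: 1 − [0.6614 + 0.1904 + 0.0246 + 0.0008 + 0.0000] = 0.123.

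| Assumed risks at 0.03/0.1/0.3/1% | P(selection above a failed dose) | Of which 0.3% fails and 1% passes |
|---|---|---|
| 1/1/1/1% | 0.004 | 0.0015 |
| 1/2/5/10% | 0.036 | 0.029 |
| 2/5/10/15% | 0.123 | 0.089 |

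Both columns assume that all four cohorts are dosed whatever is seen. Under the assumed risks, any review that stops escalation lowers them.

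**Step 4: side effect of a lower-dose condition.** Fewer than two doses then qualify unless both 0.03% and 0.1% pass, so the chance is 1 − s1s2. At 2/5/10/15% this is 1 − 0.9943 × 0.9672 = 0.038. Under the current wording it is the chance that at most one of the four doses passes.

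| Assumed risks | With lower-dose condition | Current wording, all four doses given |
|---|---|---|
| 1/2/5/10% | 0.007 | below 0.0001 |
| 2/5/10/15% | 0.038 | 0.001 |
| 5/10/15/20% | 0.143 | 0.013 |

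**The case against.** The strongest reply is that the protocol's own controls must fail first. To reach counts of 0, 0, 2, 1, the investigator and the sponsor would have to look at 2 of 6 active subjects with severe drug-related events and still report adequate safety. Appendix 4 describes Grade 3 (severe) events as medically significant, and section 5.1 calls on the safety board for medically significant suspected reactions. The board would therefore probably be engaged too. This stands, and it is why the event is unlikely. It does not repair the definition: neither review carries a numeric limit or a rule against selecting above a failed dose. The Cohort 6 review acts only after both doses have been chosen.

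A second reply is that the ordering is implied. Section 5.4 says that "each subject in Part A will receive only a single dose of SJP-0132 in an ascending fashion", and section 5.1 calls Cohort 6 the next dose level. Both suggest adjacent doses, but neither states a condition on lower doses.

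Third, section 5.5 (Justification for Dose) appears in the contents list but its body is not in the supplied text, nor is the benefit/risk section. Either could contain a dose-order rule, so the point is limited to the text available.

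Fourth, a severe event here means something disabling, warranting hospitalization or limiting self-care, after a single drop per eye. Risks of 10% or more may be far too high. That is fair, and the 1% row is given for that reason.

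A reader might go further and infer that the trial has no safeguard against escalating past a toxic dose, or that the percentages above are the chance of harm in Part B. The documents support neither. Review follows every cohort while the next is only on placebo, and the calculation leaves those reviews out.

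**Conclusion.** The point holds as a low-probability tightening of a safety rule. In the supplied text, the only numeric criterion for choosing Part B doses has no lower-dose condition. If the discretionary reviews let escalation pass a dose with 2 or more severe drug-related events, the wording can name a higher dose as the maximum acceptable dose.

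Before any review acts, the chance is well under 1% if severe events are as rare as 1% at every dose, and about one in eight at the highest risk set used for this event in the working. The true chance is lower to the extent that the reviews would stop escalation, which the documents do not allow one to quantify. The result rests on assumed risks, independent events and 6 active subjects per dose. The case for changing the text is that the written rule disagrees with the caution the reviews are meant to apply, and that the repair is cheap.

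**What to change.** In section 5.1 and the synopsis:

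1. Define the maximum acceptable dose as the highest tested dose for which that dose and every lower tested dose had no more than 1 subject with a severe (Grade 3 or higher) drug-related AE. The grade is worth stating because Appendix 4 labels only Grade 3 as severe, so a literal reader could leave out Grade 4 and Grade 5.
2. Define the second maximum acceptable dose as the next lower tested dose.
3. State what Part B does when fewer than two doses qualify: for example, one Part B dose if only one qualifies, and no Part B if none does. This belongs to the fix, because the new condition makes that situation more common.

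A numeric stop between Part A cohorts would be consistent with this but can be left to the sponsor.

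The cost is a few sentences, with no added subjects, visits or procedures. There are two downsides. The chance that fewer than two doses qualify rises as shown in the last table of the working. A chance failure at a low dose can also exclude a tolerable higher one: a dose with a true 5% risk meets the limit with probability 0.967, yet it would be ruled out if any lower dose happened to fail.
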